7.4 Demographics and Baseline Analysis

Demographic/baseline variables including age, sex, ethnicity, race, height, and weight at screening, and medical and neurological histories will be summarized using descriptive statistics for continuous variables and counts and percentages for categorical variables. Descriptive summaries will be presented by treatment group for FAS, PPS, and Safety Analysis Set.

7.5 Subject Disposition

A disposition of subjects will include the number and percentage of subjects in each of the following categories:

- Subjects in the Randomized Population
- Subjects in the FAS
- Subjects in the PP Analysis Set
- Subjects in the Safety Analysis Set

Within each of the previous categories, the number and percentage of subjects who completed and discontinued from the study and primary reason for early discontinuation

will be summarized. The reason for early discontinuation may include any of the following:

- Withdrawal of consent and assent
- Lack of efficacy
- Investigator decision
- Noncompliance with study procedures
- Occurrence of unmanageable AEs
- Lost to follow-up
- Other (study is terminated by the Sponsor, blind is broken, subject has relocated or death etc.)

7.6 Study Medication Exposure and Compliance

Duration of exposure is defined as the total number of days a subject is exposed to any study treatment. This will be calculated for each subject by taking the difference between the date of last dose minus the date of the first dose, plus 1 (date of last dose minus date of first dose +1).

Duration of treatment exposure will also be summarized using descriptive statistics.

Percent of SM Compliance is calculated as $\% \text{ compliance} = 100 * (\text{Num}/\text{Den})$, where

$$\text{Num} = \sum_{i=3}^7 \# \text{ of capsules dispensed at } \textit{visit}_i - \# \text{ of capsules returned at } \textit{visit}_{i+1}$$

$$\text{Den} = \sum_{i=3}^7 x_i \times (\# \text{ of days between } \textit{visit}_i \text{ and } \textit{visit}_{i+1}), \text{ where}$$

$$x_i = \# \text{ of capsules per day assigned to be administered at } \textit{visit}_i$$

For each treatment, SM compliance will be summarized by compliance category (< 80%, 80-120%, and >120%) and number of subjects in each compliance category. SM compliance will also be summarized as a continuous variable using descriptive statistics (n, mean, SD, median, minimum, and maximum) for each treatment.

Summaries of treatment compliance and exposure will be presented separately for the Titration Period, Maintenance Period, and combined Titration and Maintenance Periods.

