3 INVESTIGATIONAL STUDY PLAN

3.1 Overall Study Design and Plan

This is a multicenter, randomized, double-blind, placebo-controlled, 2-arm, parallel group Phase 4 study in children 6 to 11 years of age to evaluate the efficacy and safety of SPN-538 for the prevention of migraine. SPN-538 (or matching placebo) will be administered as a single oral dose QD, starting at 25 mg/day and increasing every 2 weeks in 25 mg increments to a target dose of 2 to 3 mg/kg/day or the maximum tolerated dose (MTD), whichever is less. The total study duration is a maximum of 34 weeks, including a Screening Period and a Prospective Baseline Period of up to 8 weeks; a Treatment Phase of 20 weeks (8 weeks titration followed by 12 weeks of maintenance dosing); a Dose Tapering Period of 1 to 3 weeks; and a Safety Follow up period of 1 to 3 weeks. Approximately 35 sites in the United States (US) are planned. The study schematic is shown in [Figure 1](#) and described below.

Pre-treatment Phase

Screening Period (Visit 1, up to 8 weeks before Visit 3)

At Visit 1, informed consent and informed assent (if applicable) will be obtained. Initial screening evaluation includes headache history, medical, family and psychiatric histories, ECG and vital sign assessments, physical and neurological examinations,

concomitant medications, headache disability, and laboratory tests including hematology, chemistry, urinalysis, drug screen, and serum pregnancy test (females of childbearing potential [FOCPs] only). Suicidality will be evaluated using the C-SSRS, Children's version. A visual neurological examination will also be required prior to Visit 2 ([Section 6.8.5](#)).

Subjects treated with the following prophylactic medications should discontinue the treatment 14 days prior to the Prospective Baseline Period: antipsychotics, antimanics, barbiturates, benzodiazepines amitriptyline, lithium, valproic acid, tricyclic antidepressants, AEDs, calcium channel blockers, sedatives, serotonin selective reuptake inhibitors (SSRIs), non-selective reuptake inhibitor (NSRIs), calcitonin gene-related peptide (CGRP) receptor antagonists, cannabidiol (CBD) oil, herbal preparations/supplements such as feverfew or St John's wort and/or any medications that could impair or decrease thinking and concentration. It is recommended to taper off antipsychotics, barbiturates, benzodiazepine, tricyclic antidepressants, lithium, amitriptyline, valproic acid, SSRIs and NSRIs as applicable ([Appendix 10.10](#)).

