and tolerability during this period. Additional dose titration related to body weight changes will be reviewed and approved by the Medical Monitor and the Sponsor on a case by case basis. The number, severity, and symptoms of all headaches, as well as the type and dose of rescue medication and SM compliance will be recorded daily in the Headache Diary. During the Maintenance Period, clinic visits will be scheduled every 4 weeks. During each clinic visit, a 4-week supply of SM will be provided, and SM compliance and the Headache Diary will be reviewed. Safety evaluations, including vital signs, concomitant medications, cognitive assessment, C-SSRS, clinical laboratory tests (only at Visit 8), urine pregnancy test (FOCP only), urine drug screen, physical and neurological evaluations will also be performed. [REDACTED]

[REDACTED]

During Visit 6, the eye exam will be performed, and another refresher placebo training will be administered.

Telephone contacts will occur at the intervening 2-week periods [Days 71, 99 and 127 (± 2 days)] between clinic visits for safety assessment and to provide guidance on dose reduction (as needed).

Post-Treatment Phase

Tapering Period (Weeks 21 to 23):

During the following 3 weeks the dose of SM will be gradually reduced until the subject is no longer taking the SM, so that by the end of Week 23 the subject is out of SM. Dose tapering will also be required for subjects who discontinue early during the titration period (Week 3 through Week 8) or maintenance period (Week 9 through Week 20). Subjects who discontinue early at an MTD of 25 mg/day will not undergo a dose tapering period but will return to the clinic to complete the EOS procedures (all procedures scheduled to be performed at Visit 9) within 1 week after discontinuation of SM.

End of Study (Visit 9):

[figure not shown]
All subjects who complete the study (Week 20) will return to the clinic for a final safety evaluation at the end of the Tapering Period (Visit 9). During this visit, subjects will complete the EOS procedures: clinical laboratory tests, AE assessments, vital signs, concomitant medications review, ECG, physical and neurological evaluations, eye exam, urine pregnancy test (FOCP only) and urine drug screen, headache disability, HRQoL, C-SSRS and cognitive assessments. The remaining SM and the Headache Diary device, if applicable, will be collected, and safety follow-up instructions will be provided to caregivers.

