4.3 Study Medication Dosing

The dose of SM will be flexible and optimized based on individual tolerability. The recommended target daily dose will be determined by the Investigator based on the subject's body weight and fall within the range [REDACTED] (Table 1). The maximum allowed daily dose will not exceed 100 mg/day (or four 25-mg capsules once daily); the minimum daily dose may not be less than 0.5 mg/kg/day. Individual dose recommendations will be calculated based on weight and tolerability (Table 1).

Dose optimization will be guided by clinical outcome and tolerability. During the Titration Period, subjects will be assessed during bi-weekly telephone calls, between monthly visits to the clinic, for tolerability of the SM treatment. After each telephone assessment, the Investigator will make the decision as to whether to continue increasing the dose, to maintain current dose for another 2 weeks (to allow a longer interval for dose adjustment), or to discontinue the subject early due to AEs. If a subject is to be discontinued due to AEs, an unscheduled clinic visit must be setup to perform all necessary EOS procedures.

At all dose levels, a one-step down-titration is allowed as long as the reduced SM dose does not fall outside of the allowable dose range (Table 1). Once a well-tolerated dose is achieved, the subjects will continue treatment at that dose during titration (i.e., the MTD might be achieved at Week 2 or 4 and that dose will be maintained barring any evolving AEs) until the end of Week 8. During maintenance, up to one dose reduction will be allowed for safety and tolerability. Additional dose titration related to body weight

changes will be reviewed and approved by the Medical Monitor and the Sponsor on a case-by-case basis.

Overdosage of TPM has been reported. Signs and symptoms include convulsions, drowsiness, speech disturbance, blurred vision, diplopia, impaired mentation, lethargy, abnormal coordination, stupor, hypotension, abdominal pain, agitation, dizziness and depression. Similar signs and symptoms may occur with overdosage of SPN-538. In the event of suspected OD with SPN-538, the caregiver should be instructed to call 911 and/or the local poison control center at [name].

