### 6.2. Analysis Populations

The following analysis populations are planned for this study:

- **Randomized Population:** All subjects who are randomized via the IWRS.
- **Full Analysis Set (FAS):** Subjects who are randomized, received at least one dose of

study drug and have a baseline and at least one valid post-baseline assessment of monthly migraine based on the headache diary data. The FAS will be used for all efficacy analyses with treatment classification based on the randomized treatment.

- **Per Protocol Analysis Set (PPS):** includes all subjects in the FAS who have completed Visits 1-8 with no missing MMDs and no important protocol deviations. The PPS will be used for supplementary analyses of the primary and secondary efficacy endpoints with treatment classification based on the treatment received.
- **Safety Analysis Set (SAF):** includes all subjects randomized into the study who received at least 1 dose of study medication. Data will be analyzed according to the treatment received. All safety analyses will be conducted using the Safety Population.

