### **6.10.3. Protocol Deviations**

A protocol deviation is defined as any change, divergence, or departure from the study design or procedures defined in the protocol. An important protocol deviation (IPD) is defined as a protocol deviation that might significantly affect the completeness, accuracy, and/or reliability of the study data or that might significantly affect a subject's rights, safety, or well-being.

Potential IPDs may include, but are not limited to:

- Subjects who received the study medication but did not meet all the inclusion or met any of the exclusion criteria.
- Subjects who received non-randomized study medication.
- Subject's treatment compliance < 80% or > 120%.

Prior to the database lock and break of treatment blind, potential IPDs identified in the clinical database and/or recorded in the site deviation log will be reviewed by clinical monitor and study team for the determination of IPDs, which would lead to the exclusion from the PP Population. IPDs will be summarized and listed for the randomized population.

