### **6.11. Exposure and Compliance**

Duration of exposure is defined as the total number of days a subject is exposed to study medication (SM). This will be calculated for each subject by taking the difference between the date of SM last dose minus the date of SM first dose, plus 1 (date of last dose minus date of first dose +1).

Treatment duration will be categorized in days as: completed Day 1 to  $\leq$  Day 28, completed Day 29 to  $\leq$  Day 56, completed Day 57 to  $\leq$  Day 84, completed Day 85 to  $\leq$  Day 112, completed Day 113 to  $\leq$  Day 141, and completed  $>$  Day 141. The number and percentage of subjects in each duration group will be summarized by treatment group for the Safety population.

Duration of treatment exposure will also be summarized using descriptive statistics (n, mean, SD, median, Q1, Q3, minimum, and maximum) for safety population.

Percent of study drug compliance is defined in Section 4.

[figure not shown]
[figure not shown]
For each treatment, SM compliance will be summarized by compliance category (<80%, 80-120%, and >120%) and number of subjects in each compliance category. Study medication compliance will also be summarized as a continuous variable using descriptive statistics (number and percent for each treatment).

[figure not shown]
Summaries of treatment compliance and exposure will be presented separately for the Titration Period, Maintenance Period and combined Titration and Maintenance Periods.

[figure not shown]
[figure not shown]
This analysis will be conducted for the Safety Population. Derivations of duration of treatment exposure and compliance are defined in Section 4. All study medication administration, exposure, and accountability data collected will be listed.

[figure not shown]

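### The compliance formula fixes one dose per 4-week visit interval while the dose rises every 2 weeks, so a fully adherent child titrated to 4 capsules scores about 125% in the Titration Period summary

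*Protocol*

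**What the plan says.** Protocol 7.6 and SAP Section 4 item 11 give the same formula. The numerator is capsules dispensed minus capsules returned, summed over the intervals that start at Visits 3 to 7. The denominator is x_i times the days from visit i to visit i+1, where x_i is the number "of capsules per day assigned to be administered at" visit i. Each interval therefore has one dose.

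The clinic visits fall on Days 1, 29, 57, 85, 113 and 141 (Protocol Table 2). Protocol 3.1 describes dosing as "starting at 25 mg/day and increasing every 2 weeks in 25 mg increments", and Protocol 4.3 places dose decisions between visits as well: "After each telephone assessment, the Investigator will make the decision as to whether to continue increasing the dose".

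Both documents require the result by period. In SAP 6.11: "Summaries of treatment compliance and exposure will be presented separately for the Titration Period, Maintenance Period and combined Titration and Maintenance Periods". The classes are <80%, 80-120% and >120%.

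SAP 6.10.3 lists "Subject's treatment compliance < 80% or > 120" percent among the potential important protocol deviations. SAP 6.2 restricts the Per Protocol Set to Full Analysis Set members who "completed Visits 1-8 with no missing MMDs and no important protocol deviations".

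**The concern.** In titration the dose changes in the middle of both visit intervals, around Days 15 and 43. The extra capsules a child correctly takes after each step are counted as used but never as expected, so full adherence is reported as over-use. The same inflation hides under-use, because a child who omits many capsules can still sit above 80%. A reduction directed by phone during maintenance produces a smaller error in the opposite direction.

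Two points are left open in the text available. One is whether x_4 is the dose before or after the increase made at Visit 4. The other is which of the three period values the 80%/120% screen in SAP 6.10.3 uses. At stake are the titration compliance table and, depending on the second point, who is put forward for exclusion from the Per Protocol Set.

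The size of the distortion depends on the dose reached. If the arms differ in the dose tolerated, the table could show a difference between arms that has nothing to do with adherence. That last step is an inference; the documents give no dose distribution.

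**Working it through.** The plan states no compliance result, so there is no figure of its own to reproduce. The check applies the printed formula to a child who takes every capsule.

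**Inputs**
- Visit days 1, 29, 57, 85, 113, 141 (Protocol Table 2): five intervals of 28 days.
- Start at 1 capsule, one more every 2 weeks, maximum 4 (Protocol 3.1 and 4.3): steps on Days 15, 29 and 43.
- Titration summary = intervals starting at Visits 3 and 4. The printed sum covers Visits 3 to 7 only, so this restriction is inferred from the requirement for a separate titration table.
- Base case: x_3 = 1, x_4 = dose after the Visit 4 increase.

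**Child reaching 4 capsules**
- Visit 3 to 4: taken 14×1 + 14×2 = 42; denominator 28×1 = 28; 150%.
- Visit 4 to 5: taken 14×3 + 14×4 = 98; denominator 28×3 = 84; 116.7%.
- Titration: (42 + 98)/(28 + 84) = 140/112 = **125.0%**.
- Maintenance: 336/336 = 100%.
- Combined: (140 + 336)/(112 + 336) = 476/448 = **106.25%**.

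**Other final doses, and the other reading of x_4**

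| Final dose | x_4 after the step: titration | combined | x_4 before the step: titration | combined |
|---|---|---|---|---|
| 4 capsules | 140/112 = 125% | 476/448 = 106.25% | 140/84 = 166.7% | 476/420 = 113.3% |
| 3 capsules | 126/112 = 112.5% | 378/364 = 103.8% | 126/84 = 150% | 378/336 = 112.5% |
| 2 capsules | 98/84 = 116.7% | 266/252 = 105.6% | same | same |
| 1 capsule | 100% | 100% | 100% | 100% |

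**Visit windows.** Let Visit 4 fall on Days 22-36 and Visit 5 on Days 50-64 (±7 days), with steps on Day 15, at the actual Visit 4, and on Day 43, and x_4 = 3. The 4-capsule child then ranges as follows:
- Titration: from 119/105 = 113.3% (Days 22 and 50) to 105/77 = 136.4% (Days 36 and 50).
- Combined: from 483/469 = 103.0% (Days 22 and 50) to 469/427 = 109.8% (Days 36 and 64).

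If the second step is instead held at Day 29 whatever the visit date, titration ranges from 107% to 145%.

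**What the cut-offs then mean (4 capsules, base case)**
- Titration table: a reported 120% is 120/1.25 = 96% true adherence; a reported 80% is 80/1.25 = 64%.
- Combined value: the cut-offs correspond to 80/1.0625 = 75.3% and 120/1.0625 = 112.9%. True adherence of about 75-80% passes, and 113-120% is flagged.

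**Reduction by phone.** A child going from 4 to 3 capsules on Day 71 scores (14×4 + 14×3 + 2×28×3)/(28×4 + 2×28×3) = 266/280 = 95% in maintenance with full adherence.

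**Who reaches 4 capsules.** Four capsules are 100 mg. That lies within 2-3 mg/kg from 100/3 = 33.3 kg to 100/2 = 50 kg. Eligible children of 50-60 kg meet the 100 mg cap, so they may also take 4. Protocol Table 1 is not shown, so the exact bands cannot be checked.

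**Denominator summed by day.** 14×(1 + 2 + 3 + 4) = 140, giving 140/140 = 100% in titration and 476/476 = 100% combined.

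**The case against.** The strongest reply has four parts.

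*The reading of x_i.* At Visit 3 the site hands out titration instructions, so the dose assigned there could be read as a schedule. Using the end-of-interval dose (2, then 4) gives 140/168 = 83.3% for titration and 476/504 = 94.4% combined, both inside 80-120%. This fits the words less well, since x_i is tied to the visit, and it still does not return 100%. It also moves the problem to the lower cut-off: a child missing 6 of 140 capsules would score 134/168 = 79.8%.

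*Fragility of the >120% class.* In the base case, missing 6 of 140 capsules gives 134/112 = 119.6%. With Visit 4 on Day 25 and Visit 5 on Day 57, full adherence gives 144/120 = 120.0%. Both fall in the middle class. This stands: the >120% class is likely for a fully adherent 4-capsule child, not certain. The upward bias remains in both examples.

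*The screen.* SAP Section 4 defines one compliance quantity over Visits 3 to 8, and SAP 6.10.3 most naturally means that one. On it, the fully adherent child is not flagged in any case examined. This also stands, but SAP 6.11 creates three values and SAP 6.10.3 does not choose among them.

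*Missing text and low stakes.* Some dosing text, Table 1 and parts of SAP 6.11 are redacted or not shown, so a definition of x_4 may exist there. The formula itself is printed in full in both documents. The table is descriptive, the same rule applies to both arms, flags are reviewed before unblinding, and the Per Protocol Set is supplementary. All of this limits the severity, but none of it corrects the titration table.

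**Conclusion.** The concern holds. A single dose per visit interval cannot represent a dose that changes within the interval, and none of the readings of x_i tried gives 100% in titration for a fully adherent child who was titrated upward. The main figures are 125% (titration) and 106% (combined) for 4 capsules. They assume full adherence, nominal visit days, steps on Days 15, 29 and 43, and x_4 taken after the Visit 4 increase. With x_4 taken before the increase they are 167% and 113%.

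The titration table is materially distorted. The combined value moves only modestly and affects the Per Protocol screen in marginal cases, whereas a screen on the titration value would flag fully adherent 4-capsule children. The primary analysis is not affected. This should be corrected, but it is not critical.

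**What to change.** - In Protocol 7.6 and SAP Section 4 item 11, define the denominator as the sum over days of the capsules prescribed on that day, using dated dose changes, including those made by phone.
- Confirm that those dates are captured. The phone-call procedures in Protocol 5.1.4 and 5.1.5 list concomitant medications, adverse events and dose guidance, but no dose-change date; the eCRF is not available to check. If they are not captured, add a dated dosing record. The diary can serve as a cross-check, since Protocol 3.1 says for the Maintenance Period that "SM compliance will be recorded daily in the Headache Diary".
- In SAP 6.10.3, state that the 80%/120% screen uses the combined Visit 3 to 8 value.
- If the printed formula is kept, define x_4 and footnote the titration table to say that full adherence can exceed 100%.

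The cost is wording in two documents and a small programming change, plus one dated field if phone-directed changes are not already recorded. No change to dosing is implied.

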7.7 Concomitant Medications

Prior and concomitant medications will be coded according to the World Health Organization Drug Dictionary (WHO DD) and summarized descriptively by ATC classification level 4 and preferred term for the Safety Population. Medications used within 30 days prior to the start of the study and during the course of the study will be listed. Medications with a valid stop date prior to first dose date will be considered prior

medications. Incidence (number and percent of subjects reporting the medication at least once during the study) will be summarized for all concomitant medications.

7.8 Efficacy Analysis

Based on the FAS, the observed value and change from baseline will be summarized using descriptive statistics as described in [Section 7.1](#) and presented for all efficacy endpoints by study visit and treatment group. Subject listing of the observed value and change from baseline will be listed for all efficacy endpoints. The mean profile of 28-day MMDs will be presented by treatment group and study visit.

7.8.1 Primary Efficacy Analysis

The primary efficacy endpoint, change from the Prospective Baseline Period in 28-day rate MMDs, will be analyzed using MMRM, which assumes that missing data are MAR. All post-baseline study visits will be included in the model; however, the primary comparison will be between SPN-538 and placebo at Month 5 (last 4 weeks of the Maintenance Period). The model will include fixed effect terms for 28-day rate of MMDs for the Prospective Baseline Period, treatment group, Prospective Baseline monthly migraine-specific acute rescue medication (28-day rate) use, visit, and treatment-by-visit interaction as independent variables. The model parameters will be estimated using restricted maximum likelihood method with an unstructured variance-covariance matrix and Kenward-Roger approximation to estimate denominator degrees of freedom.

If the MMRM model with the unstructured variance-covariance matrix does not converge using the default Newton-Raphson fitting algorithm by PROC MIXED in SAS, then the Fisher scoring algorithm or the no-diagonal factor analytic structure will be used (Lu & Mehrotra, 2010). If the model still fails to converge, then the first (co)variance structure which does not have convergence problem will be used for the analysis from the following ordered list:

1. Heterogeneous Toeplitz
2. Heterogeneous Autoregressive of order 1
3. Toeplitz
4. Autoregressive of order 1
5. Compound Symmetry

The denominator degrees of freedom will be estimated using the BETWITHIN option in SAS when any of the covariance structures is used with the sandwich variance estimator.

The least square mean (LS Mean) of each treatment group (placebo and SPN-538) along with the corresponding standard error, p-values, difference in the LS Mean between SPN-538 and placebo (SPN-538 minus placebo), and 95% CIs will be computed at each visit.

To assess the robustness of the primary analysis under the MAR assumption, two sensitivity analyses will be performed based on multiply imputed data assuming missing data are MNAR. The first sensitivity analysis will be based on placebo-based MI in which missing values for the subjects in the SPN-538 treatment group would adopt the outcome model estimated from the placebo arm. The second sensitivity analysis will be performed using a 'tipping point' methodology to assess the assumption of MAR in the primary analysis. The tipping point analysis will progressively impose increasing shift parameters to the imputed observations under the MNAR assumption in the active treatment arm, not to the placebo arm, to assess how severe departures from MAR must be to overturn the conclusion from the primary analysis.

The details for both approaches will be provided in the SAP.

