7.8.3 Secondary Efficacy Analyses

Secondary endpoints will be analyzed based on the FAS using appropriate statistical models based on the type of endpoints.

Analyses of Secondary Endpoints

1. Monthly Migraine Responders: For each subject, a binary response variable for change from baseline in the MMDs during the last 4 weeks of the Treatment Phase relative to baseline will be set to 'YES' if a subject's % reduction is $\geq 50\%$ or 'NO' otherwise. The proportion of responders will be presented for each treatment group. The 2-sided 95% CI around the difference in proportions (SPN-538 dose minus Placebo) and the p-value from Pearson's Chi-squared Test or Fisher's Exact Test will be presented.
2. Migraine-Specific Acute Rescue Medication: The change from Prospective Baseline in the 28-day rate of migraine-specific acute rescue medication use in the last 4 weeks of the Treatment Phase will be analyzed using the same analysis method (MMRM) as for the primary efficacy endpoint. The contrast of interest will be at Month 5 for the SPN-538 group compared with placebo.
3. Total Headache Days, Duration, and Severity: The change from Prospective Baseline in the 28-day rate of total headache days, duration of headache days (migraine and non-migraine) in the last 4 weeks of the Treatment Phase will be analyzed using the same analysis method (MMRM) as for the primary efficacy endpoint. The contrast of interest will be at Month 5 for the SPN-538 group compared with placebo.

The change from Prospective Baseline in the 28-day rate for severity in the last 4 weeks of the Treatment Phase will be summarized using descriptive statistics by severity (mild, moderate, severe, very severe).

4. Onset of action: The time to first significant treatment effect in the MMDs will be based on the MMRM analysis of the primary endpoint. The first month at which a statistically significant difference in the change from baseline in 28-day MMDs is observed and maintained until the EOS between SPN-538 and placebo will be claimed as the first month for the onset of treatment effect.
5. Headache disability: The change from baseline in the Headache Disability Score as measured by PedMIDAS during the last 4 weeks of the Treatment Phase will be summarized using descriptive statistics by visit.

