### **6.4. Adjustments for Covariates**

Where relevant, respective baseline values will be included in the statistical models as covariates.

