### **10. Changes from Planned Analysis**

There is no change from the planned analyses specified in the protocol.

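### The primary MMRM gives baseline one common slope over Months 1 to 5; if the correlation with baseline decays, some precision at Month 5 is given up, and baseline-by-visit terms would recover it at almost no cost

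*Protocol*

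**What the plan says.** Protocol 7.8.1 spells out the model: "The model will include fixed effect terms for 28-day rate of MMDs for the Prospective Baseline Period, treatment group", then baseline migraine-specific rescue use, "visit, and treatment-by-visit interaction as independent variables". The synopsis repeats the list. The only interaction is treatment by visit. On the data used, "All post-baseline study visits will be included in the model", which the visit-window table in SAP 5.1 defines as Months 1 to 5, and "the primary comparison will be between SPN-538 and placebo at Month 5". Parameters are "estimated using restricted maximum likelihood method with an unstructured variance-covariance matrix".

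Protocol 7.8.3 carries the model over to rescue-medication use, total headache days and headache duration, each of which "will be analyzed using the same analysis method (MMRM) as for the primary efficacy endpoint".

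The text of SAP 7.1 is not in the copy available for this review. The visible parts of the SAP add no interaction with baseline: section 6.4 says that, where relevant, "respective baseline values will be included in the statistical models as covariates", and section 10 states "There is no change from the planned analyses specified in the protocol".

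**The concern.** A baseline main effect fits one regression slope of change on baseline across all five months. The rest of the model is more flexible: the treatment effect may differ at each visit, and the unstructured covariance lets correlations between months take any shape. A constant relation with baseline is the one rigid part, and the design gives some reason to doubt it, since Months 1 and 2 are titration and Months 3 to 5 are maintenance.

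If baseline predicts the early months better than Month 5, the fitted slope is pulled towards the early months. Month 5 is then adjusted with a slope that does not suit it, and the misfit appears as extra Month 5 residual variance. What is at stake is precision: a wider confidence interval for the primary contrast, and for the secondary endpoints that reuse the model.

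**Working it through.** **1. The plan's own figure.** With a difference of 1.1, SD of change 3 and two-sided 0.05 (Protocol 7.9), n per arm = 2 × (1.960 + 0.842)² × 9 / 1.21 = 116.8, so 117. Exact t-test power at 117 per arm is 79.8%. Allowing for 15% dropout, 234 / 0.85 = 275.3, so 276. The plan's numbers reproduce. They refer to an unadjusted two-sample t-test.

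**2. Formula.** Let b hold the five month-specific slopes of change on baseline, and S the residual covariance given those slopes. With complete data and an unstructured covariance:

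- common slope b_c = 1'S⁻¹b / 1'S⁻¹1
- Month 5 variance with the common slope = S₅₅ + (b₅ − b_c)² × Var(baseline)
- ratio to the baseline-by-visit model = 1 + (b₅ − b_c)² × Var(baseline) / S₅₅

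**3. Assumed inputs.** None of these is in the documents: baseline SD 2.5; monthly SD 3 at every month; correlation at lag k months = c + (1 − c)rᵏ, where c is a stable between-child component. Then b_j = ρ_j × 3/2.5 − 1. With a constant monthly SD the ratio depends only on the correlations, not on the two SDs.

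| Pattern | Correlation with baseline, Month 1 → 5 | b₅ | b_c | S₅₅ | Ratio | Power, common → by visit |
|---|---|---|---|---|---|---|
| Equal, 0.5 | 0.50 → 0.50 | −0.40 | −0.40 | 6.75 | 1.00 | 84.9 → 84.9% |
| c 0.5, r 0.3 | 0.65 → 0.50 | −0.40 | −0.32 | 6.74 | 1.005 | 84.7 → 84.9% |
| c 0.4, r 0.5 | 0.70 → 0.42 | −0.50 | −0.31 | 7.42 | 1.03 | 85.6 → 86.7% |
| c 0.3, r 0.6 | 0.72 → 0.35 | −0.57 | −0.30 | 7.87 | 1.06 | 86.2 → 88.1% |
| c 0.2, r 0.7 | 0.76 → 0.33 | −0.60 | −0.24 | 7.99 | 1.10 | 85.4 → 88.5% |
| AR(1) 0.7 | 0.70 → 0.17 | −0.80 | −0.38 | 8.75 | 1.12 | 88.8 → 92.1% |
| AR(1) 0.8 | 0.80 → 0.33 | −0.61 | −0.17 | 8.03 | 1.15 | 84.1 → 88.6% |
| AR(1) 0.9 | 0.90 → 0.59 | −0.29 | 0.04 | 5.86 | 1.12 | 78.8 → 83.1% |

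Example, AR(1) 0.8: the gap is 0.434, so the excess is 0.434² × 6.25 = 1.18, and 1.18 / 8.03 = 14.7%.

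**4. Power column.** The plan's SD of 3 is for change from baseline, whereas these patterns imply an SD of Month 5 change between 2.53 and 3.57. Each pattern was therefore rescaled so that the SD of change is 3, and power was taken at 117 per arm for a difference of 1.1 (two-group t approximation). For AR(1) 0.8: the variance of change is 10.34, and the common-slope variance is 8.03 + 1.18 = 9.21. Rescaled, this is 9 × 9.21 / 10.34 = 8.02, an SD of 2.83, giving 84.1%. Gains from the interaction run from 0 to 4.5 points.

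**5. Simulation check.** The setting was 234 subjects, 3000 runs, baseline limited to 3-14 days and stratified randomization, without rescaling. Ratios of reported variance were 1.00 (equal correlations), 1.03, 1.06 and 1.14 (AR(1) 0.8). Power with the common slope against slope by visit was 90.0 and 90.0%, 85.4 and 86.6%, 81.9 and 83.1%, 79.0 and 83.7%. Mean bias was at most 0.01 day and type I error was 4.5-5.4% throughout. In the AR(1) 0.8 case the reported variance rose by 14% but the empirical variance by only 7%.

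**The case against.** A baseline main effect is a legitimate pre-specified MMRM. Randomization, stratified on baseline migraine days, protects the treatment difference whatever the slope, and the simulations show neither bias nor excess type I error. This stands: the point concerns efficiency, not validity.

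The size is also conditional. Nothing in the documents shows that the correlation with baseline decays in these children. The 15% end needs pure AR(1) decay with no stable between-child component, which the documents do not support. Under stratification, part of the penalty is conservatism in the reported variance rather than real loss. All of this stands too.

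A reader might go further and infer that the planned power falls below 80%, by inflating the variance behind that figure (79.4% at 1%, 74.0% at 15%). The documents do not support this. The 80% belongs to an unadjusted t-test with SD 3 of change, and adjustment for baseline usually more than offsets the misfit. With the SD of change held at 3, the written model has about 79-89% power in the patterns above, and only AR(1) 0.9 puts it (by one point) under the t-test's 79.8%.

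The protocol's change log attributes this model text to alignment with the SAP at the agency's request. That explains the rewrite but does not show that the common slope was considered.

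**Conclusion.** The point holds as a low-cost efficiency improvement. The listed model forces one baseline slope on five months while the test is at one of them, and no visible SAP text alters this. The excess in reported Month 5 variance is 0% if the slopes are equal, about 1-10% under moderate decay with a stable between-child component, and up to about 15% under pure AR(1) decay. The forgone gain is roughly 0-5 power points relative to the interaction model. These ranges rest on the assumed correlations, a baseline SD of 2.5 and a monthly SD of 3. The same limitation applies in form to baseline rescue use and to the secondary MMRMs, but its size there was not worked out.

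**What to change.** Before database lock, add baseline migraine-day rate by visit and baseline rescue use by visit to the fixed effects in Protocol 7.8.1 and the synopsis, and confirm that SAP 7.1 lists the same terms. In the secondary MMRMs of Protocol 7.8.3, use the respective baseline by visit. If the common slope is kept on purpose, state why.

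The cost is a line of model wording and four extra fixed-effect parameters per covariate (five visits less one), against 234 planned completers. No new data are needed. In the equal-correlation simulation the extra terms cost no power (90.0% either way).
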